**Relypsa For ED Acute Hyperkalemia Control and Reduction
(REDUCE)**

NCT 02933450

June 21st 2017

Protocol and Statistical Analysis

Study design and setting: This is a single center, single blinded, open label, feasibility pilot study performed at a large inner-city academic ED. The study was approved by the institutional review board.

Selection of participants: Patients ≥ 18 years of age and ESRD, who had serum potassium ≥ 6.0 mEq/L, were eligible for enrollment. Exclusions were: i) a significant arrhythmia on initial EKG (determined by clinical provider), ii) known allergy to patiromer, iii) an oral potassium binder administered prior to enrollment, iv) pregnancy, v) not anticipated to need medical management of hyperkalemia for at least 4 hours (i.e. hemodialysis unit and staff available for emergent dialysis and medical management is not necessary).

Interventions: After obtaining informed consent, patients were randomly assigned to standard-of-care (SOC) or a single dose of 25.2g oral patiromer plus SOC (PAT) cohort. Standard-of-care is defined as intervention provided by clinical provider according to individual practice pattern or hospital protocol. Providers were blinded to treatment assignment and all data gathered by the research team. Patients were observed with telemetry monitoring for up to 10 hours or until they received hemodialysis, whichever occurred first. Blood draws and electrocardiograms (ECGs) were performed at enrollment and at 1, 2, 4, 6 and 8hrs hours thereafter.

Outcomes: The primary outcome was the difference in serum potassium between SOC and PAT groups at 2, 4, and 6 hours. Recorded adverse events included rates of new gastrointestinal symptoms, hypomagnesemia, and hypoglycemia.

Analysis: Demographic characteristics were analyzed with Wilcoxon rank sum and Chi-squared test. Baseline serum potassium was compared using median and inter-quartile range (IQR). A mixed-effect linear regression model with an unstructured covariance structure was used to model potassium levels by adjusting for time, group interaction, and baseline potassium. The adjusted means of potassium levels over time were computed for each group. Contrasts between the two groups at each time point were evaluated and adjustment of multiple comparisons was made using Bonferroni's method. The amount of insulin and albuterol given and the number of interventions within 2, 4, and 6 hours were compared using the Wilcoxon rank sum test.

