Adverse events were reported and analyzed using Fischer's exact test or Chi squared test. Analyses were conducted per protocol basis; patients who went for hemodialysis treatment before 4hrs of medical treatment were excluded from the analysis

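### The 4-hour dialysis exclusion is not confined to the potassium analyses and no adverse-event population is named, so on its plain reading early-dialysed randomised patients drop out of the adverse-event comparison

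*Combined protocol and SAP*

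**What the plan says.** All of this is in the combined protocol and SAP.

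- **Analysis, adverse events.** The sentence beginning "Adverse events were reported and analyzed using" names Fisher's exact or the chi-squared test. It names no population.
- **Analysis, analysis set.** The next sentence reads "Analyses were conducted per protocol basis" and continues "patients who went for hemodialysis treatment before 4hrs of medical treatment were excluded from the analysis". It is not limited to potassium or to efficacy. No safety, as-treated or all-randomised set is defined anywhere.
- **Interventions, allocation.** "patients were randomly assigned to standard-of-care (SOC) or a single dose of 25.2g oral patiromer plus SOC (PAT) cohort". When the dose is given relative to enrollment is not stated.
- **Interventions, follow-up.** "Patients were observed with telemetry monitoring for up to 10 hours or until they received hemodialysis, whichever occurred first". The sampling schedule is: "Blood draws and electrocardiograms (ECGs) were performed at enrollment and at 1, 2, 4, 6 and 8hrs hours thereafter".
- **Outcomes.** The adverse events recorded are new gastrointestinal symptoms, low magnesium and low glucose.
- **Selection of participants, exclusion v.** Patients are not enrolled if they are "not anticipated to need medical management of hyperkalemia for at least 4 hours".
- **Interventions, blinding.** "Providers were blinded to treatment assignment and all data gathered by the research team".

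**The concern.** Going to dialysis early is a post-randomisation event. A 4-hour minimum has some rationale for a potassium outcome measured at 2, 4 and 6 hours. The plan gives no reason for applying it to adverse events, which can occur in any patient who has been dosed and watched, for however short a time.

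If the rule is followed as written, an early-dialysed patient leaves both the numerator and the denominator of the adverse-event rates, and leaves the between-arm tests. In the PAT arm, that patient may already have swallowed the study drug. Two things are at stake. A real event could be missing from the reported rates. And even if excluded and retained patients carry the same risk, precision is lost in a feasibility pilot that has little to spare.

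**Working it through.** The plan gives no figure to reproduce. Arm sizes, the number dialysed early and the event rates are all absent. The check is therefore mainly one of text, followed by an illustration on assumed inputs.

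**1. Does the rule reach adverse events?** The adverse-event tests come immediately before the rule. The rule's subject is the plural *Analyses*, without restriction, and no sentence exempts adverse events or gives them their own population. The plain reading includes them. The exclusion clause ends with the singular *the analysis*, which could mean the potassium model alone, but nothing in the text selects that meaning.

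**2. Can such patients exist?** Exclusion v rests on what is anticipated at entry, so it does not prevent earlier dialysis. Observation may end at dialysis, and the Analysis section has a rule for patients dialysed early. The plan thus provides for them, though it does not say that there were any.

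**3. Can they contribute safety information?** They are randomised and are observed until dialysis. Draws are scheduled at enrollment, 1 and 2 hours, before a 4-hour mark counted from enrollment. However, the exclusion clock runs on medical treatment, which may have begun before enrollment. How much observation, and how many draws, precede dialysis is therefore unknown. Whether a PAT patient had been dosed by then is also unknown.

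**4. Illustration: zero events.** The arm sizes (15 or 30) and the numbers excluded are assumptions. The one-sided 95% upper bound for an event rate after zero events in n patients is 1 − 0.05^(1/n).

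| Assumed arm | Excluded | Kept (n) | Upper bound | Bound with none excluded | Difference (points) |
|---|---|---|---|---|---|
| 15 | 1 | 14 | 19.3% | 18.1% | 1.2 |
| 15 | 3 | 12 | 22.1% | 18.1% | 4.0 |
| 30 | 2 | 28 | 10.1% | 9.5% | 0.6 |
| 30 | 6 | 24 | 11.7% | 9.5% | 2.2 |

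**5. Illustration: one event, placed by construction in an excluded patient.**

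- Arm of 15, 3 excluded: reported 0/12 = 0%; all randomised 1/15 = 6.7%.
- Arm of 30, 6 excluded: reported 0/24 = 0%; all randomised 1/30 = 3.3%.

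The loss of precision is modest, and small when few are excluded. The larger worry is the second case: with counts this low, one omitted event changes what the table says.

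**The case against.** The strongest reply is that the sponsor meant the exclusion for potassium only. The singular *the analysis* allows it, the 4-hour cut-off suits the potassium time points, and reporting events in everyone is compatible with testing them in fewer patients. This stands as a possible reading, but the text does not state it. If it was the intent, one sentence settles the matter.

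Second, few patients may be affected, because exclusion v screens out those expected to need less than 4 hours of medical management. That should reduce the number; it cannot guarantee zero. Third, blinded providers make a difference between arms in early dialysis less likely. That is fair, although it does not rule one out, and blinding does not bring back lost patients or events.

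Fourth, the illustrations rest wholly on assumed inputs, and the missed event is placed where it does most harm. That is correct: they show scale and are not evidence of an effect. Fifth, early-dialysed patients have short observation, so adding them can dilute crude rates. This stands and shapes the fix.

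A reader might go further and infer that adverse events were left unreported, that the rule favours patiromer, or that every early-dialysed PAT patient had been dosed and sampled. The documents support none of these. They do not show that anyone was excluded or that any event was omitted, and they give neither the reasons for early dialysis nor the dose timing.

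**Conclusion.** The point holds and should be fixed; confidence is medium. It is certain that the plan states an unqualified exclusion directly after the adverse-event tests and names no adverse-event population. On the plain reading, randomised and possibly dosed patients leave the safety comparison because of a post-randomisation event. Whether the rule was applied that way is uncertain, given the narrower reading.

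The size and direction of any bias cannot be derived from the documents. If risk is equal in excluded and retained patients, the cost is precision alone: about 0.6 to 4.0 percentage points on the zero-event bound in the assumed cases above. If nobody was dialysed before 4 hours of medical treatment, there is no effect.

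**What to change.** - Confine the 4-hour dialysis exclusion, in words, to the potassium (efficacy) analyses.
- Compare adverse events in all randomised patients, by randomised arm, counting from enrollment to dialysis or the end of observation.
- Report how many PAT patients received patiromer, and add a supplementary tabulation restricted to dosed PAT patients.
- Report by arm the number dialysed before 4 hours of medical treatment, their adverse events and their observation time.

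The main comparison should not be regrouped by treatment received. A PAT patient dialysed before dosing would then count as SOC. Such patients have little observed time in which to have an event, so the move would dilute the SOC rate selectively and break the randomised comparison.

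**Cost.** A few sentences in the plan and, if the analysis is already done, a re-run of the adverse-event table. This assumes that data recorded up to dialysis were retained for excluded patients, which the documents do not say. The downside is dilution of crude rates by shorter observation. Observation time by arm, or a rate per patient-hour, should therefore accompany those rates.

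### Randomised patients dialysed before 4 hours are dropped, with no all-randomised analysis beside it: the potassium contrasts may be biased and valid 2-hour primary values are lost

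*Combined protocol and SAP*

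**What the plan says.** Patients are randomised to standard of care or to patiromer plus standard of care (Interventions). Outcomes names three primary time points: "The primary outcome was the difference in serum potassium between SOC and PAT groups at 2, 4, and 6 hours". Blood is drawn at enrolment and at 1, 2, 4, 6 and 8 hours.

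The Analysis section specifies the model: "A mixed-effect linear regression model with an unstructured covariance structure was used to model potassium levels". It closes with the analysis set: "Analyses were conducted per protocol basis", followed by the rule that "patients who went for hemodialysis treatment before 4hrs of medical treatment were excluded from the analysis". No all-randomised or sensitivity analysis is described.

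Three other statements bear on the point:

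- Selection of participants, exclusion (v), bars patients who are "not anticipated to need medical management of hyperkalemia for at least 4 hours". The example given there is that a dialysis unit and staff are already available.
- Interventions: "Providers were blinded to treatment assignment and all data gathered by the research team".
- Interventions: "Patients were observed with telemetry monitoring for up to 10 hours or until they received hemodialysis, whichever occurred first".

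**The concern.** Exclusion (v) is a forecast made before randomisation. The rule in the Analysis section acts on what happens afterwards, to patients who passed that forecast and were dialysed early anyway. Removing patients for a post-randomisation event can undo the balance that randomisation provides. If patients with higher potassium go to dialysis sooner and patiromer lowers potassium, the rule removes a different kind of patient from each arm, even with providers blinded.

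A second cost does not depend on any such mechanism. A patient dialysed between 2 and 4 hours has a pre-dialysis 2-hour potassium, which is a primary value, and the rule discards it.

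At stake are the declared primary contrasts. With no all-randomised result and no count of early dialysis by arm, a reader cannot tell harmless loss of precision from bias.

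**Working it through.** **Inputs.** The documents supply the draw times, the primary time points, the model and the exclusion rule. They give no sample size, SD, effect size or early-dialysis rate, so there is no stated figure to reproduce. Every magnitude below rests on assumed inputs.

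**Step 1: what each patient contributes** (treatment and draws timed from one clock)

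| Dialysis starts | Primary values drawn before it | Under the plan |
|---|---|---|
| before the 2-hour draw | none | excluded |
| between 2 and 4 h | 2 h | excluded |
| between 4 and 6 h | 2 h, 4 h | kept, no pre-dialysis 6-hour value |
| after the 6-hour draw | 2 h, 4 h, 6 h | kept |

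The third row shows that the plan already leaves the mixed model to handle incomplete series. The second row could be handled in the same way.

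**Step 2: precision at 2 hours.** Let x be the share excluded and s the share of those dialysed before the 2-hour draw. The all-randomised set has n(1 − s·x) two-hour values and the per-protocol set has n(1 − x), so

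SE inflation = √[(1 − s·x)/(1 − x)] − 1.

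| x | s = 0 | s = 0.5 | s = 1 |
|---|---|---|---|
| 10% | 5.4% | 2.7% | 0 |
| 20% | 11.8% | 6.1% | 0 |
| 30% | 19.5% | 10.2% | 0 |

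**Step 3: bias at 2 hours.** This was simulated with 400,000 patients per scenario. Assumptions:

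- baseline potassium of at least 6.0 mEq/L;
- true effect 0.40 mEq/L at 2, 4 and 6 hours;
- residual SD 0.55 or 0.80, with correlation 0.75 per 2 hours;
- 10, 20 or 30% dialysed at 2 to 4 hours, by a logistic model in the 2-hour potassium.

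Per-protocol 2-hour estimates for SD 0.55 and 20% excluded:

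| Odds ratio per mEq/L | Estimate | Shrinkage from 0.40 |
|---|---|---|
| 1 | 0.402 | none (simulation error) |
| 2 | 0.391 | 2% |
| 3 | 0.378 | 5.5% |
| 6 | 0.361 | 10% |

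Over all rates and both SDs, shrinkage is 1 to 5% at odds ratio 2 and 3 to 22% at odds ratios 3 to 6. The worst case is 0.312 (SD 0.80, odds ratio 6, 30% excluded): (0.40 − 0.312)/0.40 = 22%. At odds ratio 1 there is no bias, even with double the dialysis odds in one arm.

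A second set of assumptions gives a similar picture: SD 0.7, correlation 0.6 between 2 and 4 hours, true effect 0.3 or 0.5, and logit slope 1 or 2 per mEq/L (odds ratios e¹ ≈ 2.7 and e² ≈ 7.4). Shrinkage is about 4 to 21% at 2 hours and 2 to 13% at 4 hours. It is nil if the true effect is zero and dialysis odds do not otherwise differ by arm.

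**Step 4: no true effect.** With SD 0.55, odds ratio 3 to 6, 20% excluded and double the dialysis odds in one arm, a false 2-hour difference of 0.03 to 0.04 appears. Its sign depends on which arm is dialysed more.

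**Step 5: does the alternative hold up if missing-at-random fails?** Let dialysis follow a 3-hour potassium that is not in the model (odds ratio 2 to 6). The all-randomised model stays unbiased at 2 hours, because that value is observed. At 4 hours it shrinks the effect by 0 to 6%, against 1 to 18% for the per-protocol set. For SD 0.80, odds ratio 6 and 30% dialysed, the 4-hour estimates are 0.376 and 0.327. If, in a separate check with SD 0.55, half of the early-dialysed go before the 2-hour draw, the all-randomised 2-hour estimate is 0.396 to 0.400.

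**Step 6: scale.** With an assumed 25 per arm and SD 0.55, SE = 0.55 × √(2/25) = 0.156. A bias of 0.04 is 0.04/0.156 ≈ 0.26 of one SE.

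**The case against.** The best defence is that the plan limits the risk. Providers do not know the arm or the research potassium values, exclusion (v) screens out expected early dialysis, and the only timing reason mentioned is dialysis availability. A strong dependence of dialysis on potassium, or unequal dialysis odds between arms, is therefore assumed and not shown. This stands as a limit on size. It does not remove the concern, because providers still treat by their own practice or hospital protocol, and nothing stops them from acting on clinical course or their own tests.

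The 4-hour limit is counted from medical treatment, whereas draws are counted from enrolment. If treatment began well before enrolment, the window in which an excluded patient has a 2-hour value narrows and could close. Exclusion (v) looks 4 hours ahead at enrolment, so one clock is the natural reading. On either reading the exclusion follows randomisation.

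The documents also do not say outright how patients dialysed between 4 and 6 hours are handled. They do fall outside the exclusion, and they cannot have a pre-dialysis 6-hour value.

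Finally, this is a feasibility pilot, so the consequence is smaller than in a confirmatory trial. That is fair. The contrasts are nevertheless its stated primary outcome.

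**Conclusion.** The concern holds and should be fixed. The exclusion acts after randomisation, no all-randomised result accompanies it, and the chosen model does not require it. Neither the size nor the direction of any bias can be read from the documents. Bias is nil if dialysis timing is unrelated to potassium. It is a few per cent of the 2-hour effect under moderate dependence, and up to about a fifth under strong dependence with 30% excluded. On the assumed pilot size, a bias of 0.04 mEq/L is about a quarter of one standard error. The loss of 2-hour values needs no bias mechanism, only that some patients are dialysed after the 2-hour draw and before the cut-off.

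**What to change.** Make the primary analysis all randomised patients in their assigned arm, with every potassium drawn before dialysis entered in the existing mixed model. The SAP should also:

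- state that post-dialysis values are treated as missing, so that the target is potassium had dialysis not occurred;
- state that the 4- and 6-hour contrasts then rely on missing-at-random, as does the 2-hour contrast for anyone dialysed before the 2-hour draw;
- report the number dialysed before 4 hours by arm;
- keep the present per-protocol set as a sensitivity analysis only;
- say which patients enter the adverse-event and the insulin, albuterol and intervention comparisons, since the exclusion is worded for the analysis as a whole.

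The cost is SAP wording, with no new data. The text is in the past tense; if the analysis has already been run, it means a re-run on values already drawn, provided those of the excluded patients were kept. The price is reliance on missing-at-random at 4 and 6 hours, which the plan already needs at 6 hours for patients dialysed between 4 and 6 hours.
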